19.2.4 Multiple Imputation

A multiple imputation will be performed based on MAR by treatment group for baseline weight, baseline and post-baseline of each parameter for visits up to 156) using Markov Chain Monte Carlo (MCMC) method with EM algorithm.

Impute the missing values 100 times (NIMPUTE) with a seed=457<studycode> as shown below:

```
proc mi data=<xxx> out=imp minmaxiter=10000000 nimpute=100 seed=4572305;
```

```
    by trt;  
    var weight_base tnf var1_base var1_week1-var1_weekx;  
    mcmc chain=multiple initial=em;  
run;
```

If needed, repeat for each component necessary to calculate the final score, e.g. as follows:

```
proc mi data=imp out=imp2 minmaxiter=10000000 nimpute=100 seed=4572305;
```

```
    by trt_imputation_;  
    var weight_base var2_base var2_week1-var2_weekxx;  
    mcmc chain=multiple initial=em;  
run;
```

All imputed variables are subject to post processing. If the imputed value is lower/greater than the absolute minimum/maximum of the parameter, then the imputed value will be set to the respective lowest/maximum possible value.

Example for Visual Analogue Scale (VAS), range=[0-100]

If the imputed value is negative then it will be set at 0

If the imputed value is greater than 100 then it will be set at 100.

For the imputation of ASAS20/40 and regarding the components of lateral lumbar flexion and CRP the following should be noted:

- Lateral lumbar flexion: if the normal distribution is not strongly violated, no transformation will be employed.
- CRP will be impute at $\ln(CRP + 1)$. Then it should be transform back.

The responses now can then be calculated based on the complete data. The response rate will be calculated for each imputation and then combined using Rubin's rules.

In order to calculate the response rate for each imputation, PROC FREQ will be used as follows.

Calculate binomial proportion and standard error for each imputation.

```
proc freq data=<ASAS20>;
```

```
  by treat visit _imputation_ ;  
  tables <response> / binomial (level=2 cl=wilson correct) ;  
  ods output BinomialProp=imp_bpr;
```

```
run;
```

Transpose the dataset for subsequent use with PROC MIANALYZE.

```
proc transpose data=imp_bpr out=imp_trs(drop=_name_) ;
```

```
  by treat visit _imputation_ ;  
  var nvalue1; id name1; idlabel labell;
```

```
run;
```

Apply LOGIT transformation: $y=\log(p/(1-p))$ and std. err. transformation: $<\text{new se}> = \text{se}/(p*(1-p))$

```
data logit;
```

```
  set imp_trs(rename=(_bin_=p e_bin=se));  
  by treat visit _imputation_ ;  
  lmean=log(p/(1-p));  
  lse=se/(p*(1-p));
```

```
run;
```

The transformed binomial proportion estimates and standard errors are combined by applying Rubin's rules for multiple imputed data sets.

```
proc mianalyze data=logit;  
  by treat visit ;  
  modeleffects lmean;  
  stderr lse;  
  ods output ParameterEstimates=logitres;  
run;
```

The combined data should be transformed back using the following formula: $p=1/(1+\exp(-y))$
data miexpress;

```
  set logitres;  
  by treat visit ;  
  resti = 1/(1+exp(-estimate));  
  rlow = 1/(1+exp(-lclmean));  
  rupp = 1/(1+exp(-uclmean));  
run;
```

Of note, sometimes all responses may be imputed to 0 or 1 at a given combination of response variable, treatment group and visit. Such cases should be considered separately. The combined final response rate would be the same as the original response but the 95% CI will be undefined.

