12.3 Handling of missing data

Missing data

Analysis of study data will be based on the observed data. In addition to the observed data approach, multiple imputation technique will be employed for the following binary variables: ASAS20, ASAS40, [REDACTED]

[REDACTED] Analysis will be limited to the higher originally randomized dose (AIN457 10 mg/kg - 150 mg)

For analyses of these parameters, if all post baseline values are missing then these missing values will not be imputed and this subject will be removed from the analysis of the corresponding variable, i.e. it might be that the number of subjects providing data to an analysis is smaller than the number of subjects in the FAS.

[REDACTED] mixed model repeated measures (MMRM) will be fitted assuming random missingness to assess the durability of secukinumab effect. The explanatory variables will be baseline score, weight,

TNF α status, analysis visit, and analysis visit by baseline score. An unstructured correlation matrix will be used thus allowing adjustment for correlations between time points within subjects. This analysis will be done on the entire treatment period for the AIN457 10 mg/kg - 150 mg treatment arm.

13 Analysis of the primary variable(s)

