13.1 Variable(s)

The primary efficacy variable is the clinical response to treatment according to the ASAS20 over time up to Week 260. The analysis of the primary variable will be based on the FAS subjects.

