13.3 Supportive analyses

[figure not shown]
Sensitivity analyses will be performed by using multiple imputation for missing assessments for ASAS20/40 to assess the robustness of missing data handling.

14 Analysis of secondary [REDACTED] variables

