14.1 Efficacy variables

Secondary [REDACTED] variables include:

- the proportion of subjects achieving ASAS40

For binary variables, the proportion of responders along with the 95% CI will be presented by groups according to the treatment sequence over analysis visits. For continuous variables, the change from core baseline will be summarized.

Results will be presented for the FAS, as well as subgroups by TNF α status (naive or IR) for the following variables: ASAS40, [REDACTED]

Graphical representation (line plots) regarding the response over time for the following measures will be provided in the observed data: ASAS20/40, [REDACTED]

[REDACTED] will also be graphically illustrated. The above mentioned figures will show the originally randomized AIN457 treatment groups.

Cumulative probability plots will be employed to display the change from baseline to week 208 illustrating the progression of subjects after 4 years [REDACTED]

Additional figures as in line plots, illustrating the up-titration effect of treatment will be created for the following parameters: ASAS20/40, [REDACTED]

ASAS20

The ASAS Response Criteria (ASAS20) is defined as an improvement of $\geq 20\%$ and ≥ 1 unit on a scale of 10 in at least three of the four main domains and no worsening of $\geq 20\%$ and ≥ 1 unit on a scale of 10 in the remaining domain.

The percentage of subjects experiencing ASAS20 response, followed by the respective 95% CI, will be presented by treatment sequence up to week 260 based on the observed data. The respective summaries will also be provided by TNF- α IR status.

Additional analysis will be based on the imputed responses only for the AIN457 150 mg group.

The percentage of subjects (and the 95% CI) experiencing ASAS20 response after up-titration will be presented in separate tables (observed data). Patients who had at least 1 dose of the up-titrated dose will be included.

[figure not shown]
ASAS40

[figure not shown]
The ASAS 40 response is defined as an improvement of $\geq 40\%$ and ≥ 2 units on a scale of 10 in at least three of the four main domains and no worsening at all in the remaining domain.

[figure not shown]
[figure not shown]
The percentage of subjects experiencing ASAS40 response, followed by the respective 95% CI will be presented by treatment sequence up to week 260 based on the observed data. The respective summaries will also be provided by TNF- α IR status.

[figure not shown]

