Additional analysis will be based on the imputed responses only for the AIN457 150 mg group.

[figure not shown]
The percentage of subjects (and the 95% CI) experiencing ASAS40 response after up-titration will be presented in separate tables (observed data). Patients who had at least 1 dose of the up-titrated dose will be included.

16 Safety evaluation

Safety analyses will be done on the safety set.

Analysis of adverse events will be based on treatment emergent events, which are defined as events started after the first dose of study treatment in core study or events present prior to the first dose of study treatment in core study but increased in severity based on preferred term and within last dose + 84 days.

Other safety variables will be based on on-treatment events, which are defined as any events that happened after first dose of study treatment and within last dose + 84 days.

Summaries (other than by visit analysis) will be presented cumulatively from core and extension. For subjects who switched from placebo to secukinumab in the core study, their data prior to switch will not be reported. Safety on placebo will be based on the core study and will be reported in the in-text outputs and study listings.

Unless otherwise mentioned, by visit analysis will include the following visits: Baseline visit from core, Week 104E1 visit and all visits in extension. Summaries will be performed for all the events that happened within the last dose + 84 days.

Safety analyses will be performed on treatment received or actual treatment as described below:

The actual treatment or treatment received for summaries of safety data will differ to the treatment assigned at randomization if a subject received the wrong treatment during the entire study or if the subject up-titrated to a higher dose..

Subjects who switch treatment during the study (e.g. from placebo to active treatment, or escalated the dose) will be counted to both groups using the corresponding start and stop exposure date.

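### The only multiple-imputation specification in the SAP stops at Week 156, although the ASAS20/40 analyses it serves carry no visit limit and the primary variable runs to Week 260

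*SAP*

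**What the plan says.** SAP 19.2.4 describes imputation under missing at random, by treatment group, for baseline weight and for "baseline and post-baseline of each parameter for visits up to 156) using Markov Chain Monte Carlo (MCMC) method". The closing bracket after 156 has no opening partner. The code beneath does not settle the range, because its first variable list is "var weight_base tnf var1_base var1_week1-var1_weekx", which ends in an open placeholder, and the second list ends the same way.

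The sections that call for the imputed analysis read differently:

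- SAP 12.3: "multiple imputation technique will be employed for the following binary variables: ASAS20, ASAS40". The restriction that follows is to the originally randomised 10 mg/kg - 150 mg arm. No visit limit is readable. For the MMRM in the same section: "This analysis will be done on the entire treatment period for the AIN457 10 mg/kg - 150 mg treatment arm".
- SAP 13.3: "Sensitivity analyses will be performed by using multiple imputation for missing assessments for ASAS20/40 to assess the robustness of missing data handling".
- SAP 14.1, for both ASAS20 and ASAS40: observed response is "presented by treatment sequence up to week 260 based on the observed data", and shortly after, "Additional analysis will be based on the imputed responses only for the AIN457 150 mg group".
- SAP 13.1: "The primary efficacy variable is the clinical response to treatment according to the ASAS20 over time up to Week 260". The primary objective in SAP 3.1 also names Week 260.

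**The concern.** A programmer who follows 19.2.4 stops the imputed ASAS20/40 tables at Week 156. One who follows 12.3, 13.3 and 14.1 carries them to the end of treatment. Both could claim to have followed the SAP, and the choice could be made after the data are seen.

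The main analysis uses observed data only, and protocol 5.5.9.4 says that withdrawn subjects are not replaced. Missing data from withdrawal can therefore only accumulate, so a check on missing-data handling is most useful at the late visits. For the binary primary variable, multiple imputation is the only such check in the readable text, since SAP 19.2.2 applies the MMRM to continuous endpoints. Under the literal rule, a Week 260 ASAS20 result would have no sensitivity analysis beside it.

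**Working it through.** No sample size, power or error rate is involved. The check is a count of visits and a comparison of sections.

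**1. Scheduled extension visits with ASAS components.** The readable components in protocol Tables 6-1 to 6-3 are the patient's global assessment and spinal pain, both on a VAS.

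| Source | Weeks | Count |
|---|---|---|
| Table 6-1 | 116, 128, 140, 156 | 4 |
| Table 6-2 | 168, 180, 192, 208 | 4 |
| Table 6-3 | 220, 232, 244, 260 | 4 |

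Total: 4 + 4 + 4 = 12. After Week 156: 4 + 4 = 8, and 8/12 = 67%. Time not covered: 260 − 156 = 104 weeks.

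**2. Does the count depend on the unreadable components?** The schedule rows for BASFI and morning stiffness cannot be read. SAP Table 19-1 offers a cross-check. Its Group 7 names the two readable components and has eight windows after Week 156, from days 1136-1219 (Week 168) to days 1766-1835 (Week 260). Group 8, whose content is blacked out, has the same eight. The two groups differ in visits covered only before Week 156: Group 7 has a Week 116 window (days 772-855) and Group 8 has none. The count after Week 156 is therefore 8 whichever of these two groups the unreadable components follow. By its title the table applies its windows only to the core study, so it is used here only as a list of visits.

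**3. Which period does the SAP serve?** SAP 8.1 refers to the final database lock at Week 260, and SAP 16.2 refers to this final lock. SAP 4 says that, in general, efficacy outputs such as the ASAS20/40 responder analysis run from Week 1 of the core study to the end of the reporting period. Protocol 9.4.3 allows imputation of efficacy variables during the trial, without a cut-off. SAP 1 says that deviations from the protocol are documented, and the readable part of SAP 2 records no Week 156 limit.

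**4. Is there a reason for stopping at Week 156?**

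- *Dose escalation.* Under protocol 5.5.5 it applies to the 75 mg arm. Imputed estimates are reported only for the originally randomised 150 mg arm (SAP 5.2 and 12.3), so escalation does not explain the limit.
- *Unblinding.* Under protocol 3.1 and 5.4 it occurs at Week 156 or when Amendment 1 is implemented, whichever is first. Week 156 is therefore the latest unblinding date and not a uniform one, and the SAP does not link imputation to it.
- *Text left from an earlier lock.* The unmatched bracket is compatible with this, but it is inference only.

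**The case against.** The best counter-argument is that this is a specific rule set against silence. No readable section says that imputation runs to Week 260. The Week 260 wording in 14.1 belongs to the observed data, and the imputed analysis is introduced as something additional. SAP 1 sends the reader to the appendix for detailed methods, so the appendix could be read as completing the body. The authors wrote out the entire treatment period for the MMRM and may have meant something shorter for imputation. Stopping early is not itself an error, since the cumulative probability plots in 14.1 stop at Week 208. Week 156 is also the end of treatment period 3. Text is blacked out beside the imputation sentence in 12.3, so a stated range may be hidden there. Finally, the protocol makes imputation optional, and SAP 4 treats confidence intervals as exploratory.

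Much of this stands as a limit on certainty and on consequence. A deliberate stop is possible, the bracket proves little, and hidden text cannot be checked. It does not remove the problem. If the limit is deliberate, 13.3 still promises a robustness check of ASAS20/40 without saying that it omits the last two years. Where 12.3 and 14.1 restrict the imputed analysis, the readable restriction is by arm. The general display rule in SAP 4 also favours the longer range, although it does not mention imputation.

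**Conclusion.** The inconsistency is real and should be fixed before the final analysis. As written, the method section leaves eight of twelve scheduled extension visits (67%), including Week 260, without an imputed ASAS20/40 estimate, while the sections that commission the analysis set no such limit.

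The consequence is bounded. Observed-data results to Week 260 do not change, no hypothesis is tested, and the imputed analysis is supportive and single-arm. The documents give no attrition figure for the extension, so neither the amount of missing data nor any bias is projected.

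The conclusion rests on the readable text. It assumes that no blacked-out passage extends or justifies the limit, and that the unreadable ASAS components follow the Group 7 or Group 8 visit pattern.

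**What to change.** In SAP 19.2.4, replace the Week 156 limit with wording such as: *for all scheduled post-baseline visits up to Week 260*. Replace the open placeholders in the variable lists so that they end at Week 260. The instruction to impute by treatment group can stay.

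If the Week 156 limit is intended, say so in 13.3, give the reason, and state that there is no imputed sensitivity result after that visit.

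The cost is a short wording change and some programming. The statistical cost is a larger imputation model, with eight more visit variables per component, which may converge more slowly in a single arm. That is a further reason to settle the range in advance.

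### Imputing each ASAS component in its own model weakens the correlation between domains and distorts the imputed ASAS20/40 rates: ASAS40 mostly low, ASAS20 low or slightly high depending on its level

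*SAP*

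**What the plan says.** The main analysis of ASAS20 and ASAS40 uses observed data (SAP 12.3 and 14.1). Multiple imputation is added for the 10 mg/kg - 150 mg arm only (SAP 12.3). SAP 13.3 gives its purpose: "Sensitivity analyses will be performed by using multiple imputation for missing assessments for ASAS20/40 to assess the robustness of missing data handling".

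SAP 19.2.4 gives the imputation code. The variable list of the first PROC MI call is "var weight_base tnf var1_base var1_week1-var1_weekx": weight, TNF status, and one component's baseline and visits. The section continues "If needed, repeat for each component necessary to calculate the final score, e.g. as follows", and the repeat call has the list "var weight_base var2_base var2_week1-var2_weekxx". It reads the first call's output, but the first component is not in its list. Afterwards, "The responses now can then be calculated based on the complete data".

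The response rules are in SAP 14.1. ASAS20 needs a gain of at least 20% and 1 unit "in at least three of the four main domains and no worsening of" that same size in the remaining domain. ASAS40 needs a gain of at least 40% and two "units on a scale of 10 in at least three of the four main domains and no worsening at all in the remaining domain".

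**The concern.** A response depends on how the four domains move together in one patient at one visit. An imputation model for such a composite should preserve that association. Here each component is drawn from a model that contains none of the others.

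- After dropout all four domains are missing together. The imputed response then rests wholly on four draws linked only through the patient's past values.
- If a single domain is missing at a visit, the three observed at that visit are ignored.

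The resulting shift comes from the imputation structure and not from the missing data. Multiple imputation is the only missing-data sensitivity analysis that the SAP names for ASAS20/40. A model-made gap between imputed and observed rates could be read as a missing-data effect, or could mask one. Correcting other details of the code (number of imputations, seed, the TNF term, the visit limit) would not remove this.

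**Working it through.** The SAP gives no imputed rate or expected bias, so there is no plan figure to reproduce.

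**1. Limiting cases.** Suppose each domain improves with the same probability p, and ignore the no-worsening condition. Under independence, P(at least 3 of 4) = 4p³(1 − p) + p⁴ = 4p³ − 3p⁴. Under perfect correlation it equals p.

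| p | Independent | Perfectly correlated |
|---|---|---|
| 0.5 | 31.3% | 50% |
| 0.6 | 4(0.216) − 3(0.1296) = 47.5% | 60% |
| 0.7 | 65.2% | 70% |
| 0.8 | 81.9% | 80% |
| 0.9 | 94.8% | 90% |

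The two are equal at p of about 0.77. Losing correlation lowers the rate below that point and raises it above. The direction therefore depends on the response level.

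**2. Simulation.** There were 60 scenarios of 300,000 subjects, with four 0-100 domains, baseline plus five visits, and the last two visits missing in dropouts. The last visit was imputed (a) from each component's own history, as in SAP 19.2.4, and (b) jointly from all four. Values were clipped to 0-100 and the SAP 14.1 rules applied.

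These inputs are assumptions, not figures from the documents: between-domain correlation 0.5, 0.7 or 0.85; between-visit correlation 0.5 or 0.7; 20% missing, either completely at random or at random with worse patients leaving; baseline mean 66, SD 15; post-baseline SD 24. Weight and TNF status were left out. The documents' only anchor is ASAS20 of about 60% at Week 16 (Protocol, Amendment 1 rationale), so a range of true rates was used.

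Bias in the overall rate with separate models, 20% missing:

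| True ASAS20 | Bias (points) | True ASAS40 | Bias (points) |
|---|---|---|---|
| 56-61% | −0.5 to −1.8 | 29-36% | −1.0 to −2.8 |
| 72-74% | 0.0 to −0.8 | 45-51% | −0.9 to −2.7 |
| about 82% | −0.3 to +0.4 | 58-62% | −0.5 to −2.0 |
| 88-89% | +0.2 to +0.8 | 70-72% | −0.1 to −1.0 |
| 93-94% | +0.4 to +0.9 | about 80% | −0.1 to +0.5 |

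One scenario in full (missing at random, between-domain correlation 0.7, between-visit 0.5): among dropouts the true rates were 49.5% (ASAS20) and 24.1% (ASAS40). Separate models gave 41.6% and 12.1%; joint imputation gave 49.5% and 23.0%. The overall bias with separate models is 0.20 × (41.6 − 49.5) = −1.6 points for ASAS20 and 0.20 × (12.1 − 24.1) = −2.4 points for ASAS40.

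Across all scenarios:

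- Joint imputation left −0.1 to +0.6 points for ASAS20 and −0.2 to +0.5 for ASAS40. The upward remainder comes from the normal model with clipping.
- Between-domain correlation of separately imputed values was 0.17 to 0.53, against 0.46 to 0.85 in truth.
- Bias scaled roughly with the missing share: about half at 10%, about double at 40%.

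**3. Smaller simulation.** With 95 subjects, 12 extension visits, about 22% missing at the last visit and three scenarios, ASAS40 was 1.8 to 3.2 points low at a true 47-48%, in line with the table. ASAS20 was 1.2 to 1.9 points low at about 71%. That exceeds the 0.0 to −0.8 found at 72-74% in the large simulation, so I do not rely on it.

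**The case against.** **The code is only an example.** It is introduced conditionally and as an illustration. But the text available gives no joint model anywhere else, and this code is the only operational specification.

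**The draws are not unrelated.** A reader might infer that they are. The documents do not support that: each draw is conditioned on the domain's own observed history, and those histories are correlated. Extension subjects also bring two years of core-study visits. The correlation is weakened, not removed. This objection stands.

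**ASAS20 need not be biased low.** A reader might also infer that both rates are too low. That fails for ASAS20 at high response levels. The 60% anchor is an early rate in the randomised population. The extension enrols core completers judged to benefit and excludes those who do not (Protocol 4.1 and 4.2), so a higher long-term rate is plausible, though none is given. This objection stands too.

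**It matters little.** Only exploratory estimates in one arm are affected, and no hypothesis is tested (SAP 4 and 13.2). For scale, 279/0.75 and 316/0.85 both give about 372 core subjects. If there were three equal core arms (an assumption), about 93 to 105 per arm would enter. At n = 95 the 95% half-width is 1.96 × √(0.71 × 0.29/95) = 9 points for ASAS20 and 1.96 × √(0.475 × 0.525/95) = 10 points for ASAS40. The shifts are well inside that. This limits the severity, but a systematic shift in a robustness check is still avoidable.

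**Conclusion.** The defect holds in a limited form. Separate component models weaken the same-visit correlation between domains, so the ASAS20/40 multiple-imputation rates in the 10 mg/kg - 150 mg arm are distorted by the imputation structure. At about 20% missing, ASAS40 is mostly low, by roughly 1 to 3 points at true rates of about 30% to 50% and by less at higher rates. ASAS20 is low by about 0.5 to 2 points near 60%, close to zero at about 72% to 82%, and high by under 1 point from 88%.

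The mechanism can be read directly from the SAP. The sizes rest on assumed correlations, score distributions and missing share, and the direction for ASAS20 rests on a long-term rate that the documents do not state. It would go too far to say that the primary result is biased or that the sensitivity analysis is worthless: the observed-data analysis is untouched, and the shift is small beside the sampling error. I rate this as a cheap improvement, between minor and something that should be fixed.

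**What to change.** Replace the separate calls in SAP 19.2.4 with a fully conditional specification (FCS regression) in which the components inform each other. Each component's model at a visit should include weight, TNF status, its own baseline and history, the other components at the same visit (observed or already imputed), and a short summary of their history, such as the last value and the mean of earlier visits.

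Keep the predictor set small for the arm size; about 10 to 15 is reasonable for about 95 subjects. One multivariate-normal model over everything is too large: the 12 extension visits with global assessment and spinal pain (Protocol Tables 6-1 to 6-3) would give 4 × 12 = 48 variables if all four components are taken at each, before baselines and core visits.

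SAP 19.1 allows gaps in visits, so a scheme that only moves forward in time is not enough. Fill intermittent gaps using later observed visits as well (FCS or MCMC) before any monotone step. Then derive ASAS20/40 and combine as already written. The simulations tested joint imputation under dropout only, so the handling of gaps should be checked on the programmed version.

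The cost is SAP wording and a longer imputation program for one sensitivity analysis. No data collection changes.

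### SAP 19.2.4 specifies 100 imputations, but its template for the second and later components imputes 100 times again inside each of them

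*SAP*

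**What the plan says.** The instruction in SAP 19.2.4 is "Impute the missing values 100 times (NIMPUTE" option of PROC MI), with one seed built from the study code. The pooling rule follows: "The response rate will be calculated for each imputation and then combined using" Rubin's rules.

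The code for the first component agrees: "proc mi data=<xxx> out=imp minmaxiter=10000000 nimpute=100 seed=4572305", run by treatment, with the variable list "var weight_base tnf var1_base var1_week1-var1_weekx".

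For each further component needed for the score, the SAP prints a second call: "proc mi data=imp out=imp2 minmaxiter=10000000 nimpute=100 seed=4572305". Its input is the output of the first call, its BY line names treatment and `_imputation_`, and its variable list is "var weight_base var2_base var2_week1-var2_weekxx", without `tnf`.

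The analysis code then computes the response proportion by treatment, visit and `_imputation_`, and pools it by treatment and visit in "proc mianalyze data=logit". The scope of the imputation is "baseline and post-baseline of each parameter for visits up to 156".

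SAP 13.3 names multiple imputation as the sensitivity analysis for ASAS20/40. SAP 12.3 restricts it to the arm originally randomized to 10 mg/kg - 150 mg. SAP 14.1 defines both responses over four main domains.

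**The concern.** ASAS20 and ASAS40 are composites of four domains, so the second call is the one that operates for the primary variable, up to three times in sequence. Each use multiplies the number of completed data sets by 100, while the text still speaks of 100 in total. The printed code neither reduces the nested copies to 100 nor gives them a second index.

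The programmer must therefore decide how the nested copies are labelled, and that decision can matter a great deal or hardly at all. Multiple imputation is the only method SAP 13.3 names for testing the robustness of missing-data handling. A check of that kind should not depend on an unstated choice in its own template.

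The loss of `tnf` from the second list is a smaller matter. TNF status is a covariate in the mixed model fitted to the same arm (SAP 12.3 and 19.2.2) and defines the planned ASAS20/40 subgroups (SAP 13.2 and 14.1).

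**Working it through.** **Inputs**
- Stated imputations: 100 (SAP 19.2.4).
- `nimpute`: 100 in both printed calls (SAP 19.2.4).
- Components: four main domains for ASAS20/40 (SAP 14.1).
- Illustrative response p = 0.60: the approximate Week 16 ASAS20 rate in the 10 mg/kg - 150 mg arm (Protocol, Amendment 1 rationale).
- Arm size: not given for the extension. I assume n = 100, with a range of 80 to 125.
- The printed BY line of the second call lacks a space. I read it as treatment and `_imputation_` and do not count the space as an error.

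**Step 1: number of completed data sets.** The count is the product of `nimpute` over the chained calls.
- One component: 100, which reproduces the stated figure.
- Two: 100 × 100 = 10,000.
- Three: 100^3 = 1,000,000.
- Four: 100^4 = 100,000,000.
- With `nimpute=1` after the first call: 100 × 1 × 1 × 1 = 100, as stated.

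If the arm is one third of the 279 to 316 subjects expected (assumed; 93 to 105), four components read literally give 9.3 to 10.5 billion subject records. That is not practical to run.

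**Step 2: copies pooled as distinct sets.** The nested version, pooled as 10,000 distinct sets, was simulated in two scenarios of 150 replicates each with assumed score distributions. The interval half-width was 9.74 against 9.73 points in one and 10.06 against 10.06 in the other, a change of at most 0.01 points.

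**Step 3: copies sharing one `_imputation_` value.** PROC FREQ would then see 100 rows per subject after one nested call. The formulas are SE = sqrt(p(1 − p)/(n × copies)) and, as in the SAP, logit SE = SE/(p(1 − p)).
- One row per subject: SE = sqrt(0.24/100) = 0.0490; logit SE = 0.0490/0.24 = 0.204; complete-data 95% interval 50.1% to 69.1%.
- 100 rows per subject: SE = sqrt(0.24/10,000) = 0.0049; logit SE = 0.0204; interval 59.0% to 61.0%.
- Over n = 80 to 125: SE 0.055 to 0.044 becomes 0.0055 to 0.0044.

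The factor is sqrt(100) = 10 for every nested call. A simplified simulation imputed the response directly (n = 100, p = 0.60, 10% to 30% missing). Coverage of the pooled 95% interval was about 95% to 96% with one copy per imputation and about 7% to 9% with 100 stacked copies.

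**Step 4: `tnf`.** In simulation with the 30% TNF-IR share of Protocol 3.1 and an assumed 10 mm shift, leaving `tnf` out moved the arm's response rate by at most 0.14 points.

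**The case against.** The best defence is that the second call is offered as an example to be used where needed, and that the governing text fixes 100 imputations with one rate for each. An experienced programmer would probably set `nimpute=1` unprompted. The 100,000,000 figure also extrapolates to calls that are not printed. This lowers the likely harm but does not remove the mismatch. A four-domain response needs the repeated call, and the code gives literal option values that contradict the text.

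Three stronger readings are tempting, and the documents do not support them.

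- **A reader might infer that the imputed intervals will be ten times too narrow.** That follows only if nested copies share one `_imputation_` value. The documents do not say how they are labelled, and SAS behaviour was not tested.
- **A reader might infer that the repeated seed is a second contradiction.** It follows the SAP's own single-seed rule. Whether it links draws across components is not established, so a change of seed cannot be called free of statistical consequences. Under assumed correlations and 5% to 20% missing, imputing components separately instead of jointly moved whole-arm ASAS40 by −3.6 to 0.0 points with independent draws and −0.6 to +2.0 with shared draws.
- **A reader might infer that imputing each component without the others is an error.** It is a modelling choice. The figures just given rest on correlations and dropout patterns the documents do not supply, and even their direction is not assured.

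On `tnf`, neither the text of SAP 19.2.4 nor Protocol 9.4.3 names TNF status for the imputation model. The omission is therefore an inconsistency between two calls and does not bear on the stated number of imputations.

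**Conclusion.** The point holds as a mismatch between text and code: 100 imputations are stated, and 100^k are requested for k components. Confidence in the mismatch is high because it rests on the printed options alone. Its effect on results is unresolved. It runs from a half-width change of at most 0.01 points (distinct sets, simulated) to a within-imputation standard error 10 times too small per nested call (shared index). The illustrative standard errors assume n of 80 to 125 and a 60% response.

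Severity is minor. The analysis is supportive (SAP 13.3), confined to one arm (SAP 12.3), exploratory (SAP 4) and, as specified in SAP 19.2.4, limited to visits up to Week 156. A reader might infer that the primary ASAS20 summary to Week 260 is compromised. It is not: that summary uses observed data, which this template does not touch.

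**What to change.** - In every PROC MI call after the first, set `nimpute=1` and run by `trt _imputation_`, so that exactly 100 completed data sets are pooled.
- State that ASAS20 and ASAS40 are derived once per imputation, after all components are complete.
- Carry `tnf` in every variable list, as in the first call, and name TNF status in the text of SAP 19.2.4.

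These are template edits. They need no new data, and the `nimpute` and `tnf` changes have no statistical downside.

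The sponsor may also consider, as optional modelling choices, a stated seed for each call and the inclusion of already imputed components from the same visit in later variable lists. The latter adds up to three terms per visit in an arm of perhaps 93 to 105 subjects (assumed), so model stability would need checking. Neither is needed to resolve the contradiction.
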